### **5.2.2.1 Recommended prophylaxis**

To reduce the severity of symptoms associated with CMP-001 induced cytokines, prophylaxis is strongly recommended. Prophylactic regimens already in place at institutions should be followed, if not, below is a suggested regimen that has been effective for the treatment of CMP-001 induced adverse events:

- Fluids (e.g. 1000 cc IV normal saline)
- NSAIDS (e.g. 1000 mg acetaminophen and 50 mg Indomethacin)
- Anti-emetics (e.g. 8 mg Zofran PO)
- Hydrocortisone prophylaxis (50-100mg hydrocortisone – only for patients with prior G2-3 CRS-like reaction)

If an Investigator incorporates prophylaxis, administration should occur 30 minutes prior to intra-tumoral injection of CMP-001. It is also highly recommended to continue to run additional fluids immediately following the CMP-001 injection, rather than waiting to initiate fluids when hypotension is detected. There is no waiting period between the end of prophylaxis and the start of CMP-001 intra-tumoral injection. All treatments given prophylactically pre-and post CMP-001 dosing should be recorded on the Prior and Concomitant Medications eCRF separately for each visit where it is given.

**IMPORTANT:** Subjects with a history of adrenal insufficiency are at increased risk for moderate to severe adverse events such as hypotension which may occur with 1-4 hours after injection. It is strongly recommended that these subjects receive stress dose steroids (eg. 50-100 mg hydrocortisone PO q 8 hours) prior to, or immediately after injection of CMP-001.

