**Table 7.2.2.2-1: Classifications for Adverse Event Causality/Relationship**

Classification	Definition
Unrelated	There is no suspicion of a causal relationship between exposure to the study drug regimen and the AE; another cause of the AE has been identified, no temporal association with study drug has been identified, or the study drug cannot be implicated.
Possibly related	There is some evidence supporting the possibility of a causal relationship between study drug regimen exposure and the AE; an alternative explanation (i.e., concomitant drug or concomitant disease) is inconclusive, the temporal association with study drug is reasonable, and the causal relationship cannot be excluded.
Probably related	An adverse event that has a timely relationship to the administration of the investigational drug regimen and follows a known pattern of response, but for which a potential alternative cause may be present.
Definitely related	There is strong evidence that there is a causal relationship between study drug regimen and the AE; the AE cannot be reasonably explained by an alternative explanation (i.e., concomitant drug or concomitant disease) and the temporal association with study drug is suggestive of a causal relationship.

An AE is considered related to treatment if the attribution is “possibly related”, “probably related”, or “definitely related.”

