##### 7.2.3.1 Treatment-related AE

Treatment-related AE/SAE is defined as an AE that started or worsened in severity on or after the date the study drug was first administered. TEAE information will be collected from the time of the subject's first receipt of CMP-001 until 30 days after the last dose of CMP-001.

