#### 7.2.4 Recording Adverse Events/Serious Adverse Events

All AEs and SAEs experienced by a subject will be recorded on the appropriate eCRF. Information including a concise description of the event; date and time of event onset and resolution; determination of seriousness, severity, corrective treatment, outcome, relationship to study drug; and action taken regarding the study drug will be recorded. Vital signs, laboratory results, and other safety

assessments noted in **Section 7.1.2** will be recorded as AEs if they are determined to be clinically significant findings in the opinion of the Investigator. When possible, a diagnosis should be recorded as an AE, rather than symptoms or isolated laboratory abnormalities related to that diagnosis. However, when flu-like or cytokine release-like symptoms are reported, each individual symptom should be recorded as a separate AE in the Electronic Data Capture (EDC) system. A medical or surgical procedure is not an AE; rather the condition leading to the procedure should be recorded as the AE. If the condition is not known, the procedure must be recorded as an AE instead. Similarly, death is not an AE, but is rather the outcome of the AE(s) that resulted in death. If the AE(s) leading to death are not known, then death must be reported as an AE.

All SAEs experienced by the subject will be entered into the CTMA and reported to the Sponsor or designee, in accordance with Section **7.2.5.1**.

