### **8.5 Safety Analysis**

As per NCI CTCAE Version 4.0, the term toxicity is defined as adverse events that are classified as either possibly, probably, or definitely related to study treatment. The maximum grade for each type of toxicity will be recorded for each patient, and frequency tables will be reviewed to determine toxicity patterns.

As CMP-001 has previously been dose-escalated in combination with PD-1 inhibitors pembrolizumab and nivolumab with minimal additional toxicities, no “dose-escalation” will be performed in this study. However, to accurately capture toxicities for this novel combination, we will be monitoring toxicities closely. The detailed data and safety monitoring plan is in **Section 8.7**.

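### The safety table in 8.5 will have no row for cytokine-release-like reactions, because 7.2.4 records them symptom by symptom; separately, 7.2.3.1 labels a treatment-emergent definition as treatment-related

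*Combined protocol and SAP*

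**What the plan says.** **Recording of cytokine-release-like reactions.** Section 7.2.4 states a general rule: "When possible, a diagnosis should be recorded as an AE, rather than symptoms or isolated laboratory abnormalities related to that diagnosis". It then makes an exception: "when flu-like or cytokine release-like symptoms are reported, each individual symptom should be recorded as a separate AE". For each event the site also enters onset and resolution dates and times and the "determination of seriousness, severity, corrective treatment, outcome, relationship to study drug".

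**How the protocol treats the reaction elsewhere.** Section 5.2.2.1 offers one prophylaxis step "only for patients with prior G2-3 CRS-like reaction", so it assumes that someone has graded the reaction as a whole. Section 5.2.2.7 lists the expected symptoms (fever, nausea or vomiting, chills or rigors, hypotension), names the syndrome under its own sub-heading and refers to a treatment algorithm. Section 7.2.5.2 lists two events of clinical interest, overdose and cutaneous injection-site events. Cytokine release is not among them.

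**Analysis.** Section 8.5 defines toxicity by attribution to study treatment (possibly, probably or definitely related) and says: "The maximum grade for each type of toxicity will be recorded for each patient".

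**Definition of treatment-related.** Section 7.2.3.1 says: "Treatment-related AE/SAE is defined as an AE that started or worsened in severity on or after the date the study drug was first administered". Its next sentence begins: "TEAE information will be collected from the time of the subject's first receipt of CMP-001". The note under Table 7.2.2.2-1 gives a different rule: "An AE is considered related to treatment if the attribution is" possible, probable or definite.

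**The concern.** Safety is a secondary objective (3.2), and the CRS-like reaction is the CMP-001 risk to which the protocol gives most attention. A reader of the final report will want to know how many patients had one and how severe it was. If the entries are symptoms only, the 8.5 table answers this for fever, for chills and for hypotension, each alone. A patient with all three after one injection appears in three rows, and nothing shows that they were one reaction.

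The second matter is one of definition. Surgery follows the Prime Phase, so under the wording of 7.2.3.1 a new post-operative complication judged unrelated would still carry the label treatment-related. Under 7.2.2.2 it would not. Anyone who programmed an output called treatment-related from 7.2.3.1 would obtain a different numerator from one who followed 7.2.2.2.

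**Working it through.** **Step 1. Is there a syndrome-level record anywhere?**

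| Place | What it provides |
|---|---|
| 7.2.4 | Symptoms entered in place of the diagnosis; no linking field |
| 7.2.5.2 | Cytokine release not an event of clinical interest |
| 8.2 | DLT criteria by individual event and grade |
| 8.5 | Maximum grade per toxicity type; no grouped term, no time window |
| 5.2.2.1 | Refers to a reaction grade, but creates no AE entry |
| 5.2.2.7 | Symptom list, usual onset 1 to 4 hours after injection, treatment algorithm; no AE entry |

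Nothing in the text supplies the record or the derived variable.

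**Step 2. Are the symptom rows wrong?** No. Section 8.5 takes one maximum grade per type per patient, so a patient counts once in each row, and splitting a reaction into symptoms does not inflate any row.

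**Step 3. What can be read from symptom rows alone?** The plan gives no CRS-like rate, so I use Table 4.1.4-1 (the earlier pembrolizumab combination study, weekly schedule, N=28) as illustration. The six relevant rows are fever 16, chills 15, hypotension 8, nausea 8, vomiting 8 and rigors 6.

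- The table's own percentages reproduce: 16/28 = 57.1%, 15/28 = 53.6%, 8/28 = 28.6%, 6/28 = 21.4%.
- Total entries: 16 + 15 + 8 + 8 + 8 + 6 = 61, or 61/28 = 2.18 per patient.
- Patients with at least one symptom: the lower bound is the largest row, 16/28 = 57.1%; the upper bound is min(28, 61) = 28/28 = 100%.
- Patients with at least two symptoms, lower bound: if only k patients have two or more, they absorb at most min(row, k) entries of each row, and the rest must fit one each into the other 28 − k patients.
  - k = 6 leaves 10 + 9 + 2 + 2 + 2 + 0 = 25 entries for 22 patients, which is impossible.
  - k = 7 leaves 9 + 8 + 1 + 1 + 1 + 0 = 20 entries for 21 patients, which fits. The lower bound is 7/28 = 25.0%.
- Patients with at least two symptoms, upper bound: 28/28, since 61 ≥ 2 × 28 = 56 and no row exceeds 28.
- Patients with both fever and hypotension: from max(0, 16 + 8 − 28) = 0 to min(16, 8) = 8, that is 0% to 28.6%.

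A table of this form does not determine the syndrome rate. The bounds describe published marginal counts. They do not bind this trial, which will hold patient-level records.

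**Step 4. Does DLT review lose anything?** Under 8.2 a related non-laboratory toxicity of Grade 3 or higher is a DLT, so a symptom of that grade is seen individually. What is absent is a grade for the reaction as a whole.

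**Step 5. Does 7.2.3.1 alter 8.5?**

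| Place | Basis of the definition |
|---|---|
| 7.2.2.2 (note under the table) | Attribution |
| 8.2 (DLT) | Attribution |
| 8.5 (toxicity) | Attribution |
| 8.7 (IRB reporting) | At least possibly related |
| 7.2.3.1 | Timing only |

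Section 8.5 states its own rule and does not cite 7.2.3.1. Applied as written, the change in 8.5 counts is zero. Had 7.2.3.1 been used, every treatment-emergent event judged unrelated would be added; the documents give no figure for how many.

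**The case against.** A reader might infer that the two rules distort the toxicity counts in 8.5. The documents do not support that: each symptom row is a correct per-patient count (step 2), and 8.5 selects by attribution (step 5).

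A reader might also infer that the reaction can never be reported, or that serious reactions escape notice. That goes too far as well. Section 7.2.4 does not forbid a syndrome entry in addition to the symptoms. Dated and timed symptom records, with grade and relationship, allow a composite to be derived. Seriousness is recorded per event and is distinct from severity (7.2.2.1), and SAE reports carry terms, grades and interventions (7.2.5.1).

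It can be added that symptom-level recording matches the form of Table 4.1.4-1 and so keeps comparability, that the prophylaxis criterion in 5.2.2.1 is a bedside judgement needing no eCRF row, and that neither the eCRF nor Figure 4 is available here. The first is a good reason to keep the symptom rows. The second is fair, but it does not supply a number for the report. On the third, a management grading in Figure 4 would not by itself create an AE record, although an eCRF field might already exist.

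What remains is that any composite would rest on a grouping rule and a time window that the plan does not state and that would be chosen after the data are seen. The 7.2.3.1 point is a label slip, as the abbreviation TEAE in its next sentence shows, but it still contradicts 7.2.2.2.

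**Conclusion.** The gap is real and inexpensive to close. Following 7.2.4, the 8.5 table will not show the number and grade of patients with a CRS-like reaction, and no derivation is prespecified. No existing row is biased, DLT review still sees symptoms of Grade 3 or higher, and the primary endpoint is unaffected. No rate for this trial can be given; the range of 57.1% to 100% illustrates the limits of marginal counts in another study, in patients with checkpoint-resistant disease.

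The contradiction between 7.2.3.1 and both 7.2.2.2 and 8.5 is definite, with no effect on 8.5 as written. It would matter only if an output were built from 7.2.3.1.

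The conclusion assumes that the exception in 7.2.4 means symptoms instead of the diagnosis, which is its natural reading, and that no unseen eCRF field already links the symptoms.

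**What to change.** 1. Keep the symptom rows. Add one linked AE record, CRS-like reaction, with its own grade and the CMP-001 dose number.
2. If the eCRF cannot change, prespecify a grouped term in 8.5: the symptoms listed in 5.2.2.7 with onset in a stated window after injection, graded by the maximum component grade. This recovers a patient count, but not an investigator-assigned grade of the reaction.
3. In 8.5, report patients with any-grade and with Grade 3 or higher CRS-like reactions, each with an exact 95% confidence interval.
4. Rename 7.2.3.1 to treatment-emergent AE, leaving 7.2.2.2 as the only definition of relatedness.
5. Have 8.5 tabulate all treatment-emergent events alongside those attributed as possibly, probably or definitely related. At present it tabulates only the attributed ones.

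Cost: one eCRF entry or one derived variable, and slightly longer safety tables. Nothing in dosing, management or sample size changes.

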## **7.2.5 Reporting Serious Adverse Events and Serious Unexpected Adverse Events**

### **7.2.5.1 SAE and SUAE Reporting**

All events meeting the definition of a serious adverse event should be recorded on a MedWatch 3500A Form

(<http://www.fda.gov/downloads/AboutFDA/ReportsManualsForms/Forms/UCM048334.pdf>) or departmental SAE form. Copies should be sent to:

- Principle Investigator (and Sponsor)
- The Checkmate Drug Safety contact information is available for SAE reporting on a 24-hour basis and is reviewed during normal business hours. The contact information is as follows:  
**Email:** [[contact]](mailto:[contact])
- The Bristol-Myers Squibb Drug Safety contact information is available for SAE reporting on a 24-hour basis and is reviewed during normal business hours. The contact information is as follows:  
**Email:** [[contact]](mailto:[contact])
- UPMC Institutional Review Board per institutional reporting requirements
- In addition to completing appropriate patient demographic and suspect medication information, the report should include as applicable the following information that is available at the time of report within the Event Description (section 5) of the MedWatch 3500A form or departmental SAE form:
  - CTCAE term(s) and grade(s)
  - Current status of study drug
  - Intervention(s) to address the AE (testing and result, treatment and response)
  - Hospitalization and/or discharge dates
  - Event relationship to study drug combination

### **7.2.5.2 Events of Clinical Interest**

Selected non-serious and serious adverse events are also known as Events of Clinical Interest (ECI) and must be reported within 24 hours to the Sponsor and within 2 working days to Checkmate Drug Safety Contact (see **Section 7.2.5.1**).

For the time period beginning when the consent form is signed until treatment initiation, any ECI, or follow up to an ECI, that occurs to any subject must be reported within 24 hours to the Sponsor and within 2 working days to Checkmate Drug Safety Contact if it causes the subject to be excluded from the trial, or is the result of a protocol-specified intervention, including but not limited to washout or discontinuation of usual therapy, diet, placebo treatment or a procedure.

For the time period beginning at treatment initiation through 90 days following cessation of treatment, or 30 days following cessation of treatment if the subject initiates new anticancer therapy, whichever is earlier, any ECI, or follow up to an ECI, whether or not related to Checkmate product, must be reported within 24 hours to the Sponsor and within 24 hours to Checkmate Drug Safety Contact.

Events of clinical interest for this trial include:

- An overdose of Checkmate product
- Cutaneous adverse events at the injection site

#### **7.2.5.3 Pregnancies**

Female subjects or the partners of male subjects who discover they are pregnant within a year of their last CMP-001 dose will be instructed to notify the Investigator immediately.

If the Investigator learns of a report of pregnancy at any time after signing the ICF, the Investigator must complete a Pregnancy Form and report the pregnancy to Checkmate Pharmaceuticals Drug Safety within 24 hours (following the same reporting process outlined in **Section 7.2.5.1**).

The Investigator will inform the subject that the Sponsor or its designee is required to gather information regarding the course and outcome of a pregnancy that has occurred after exposure to a study drug. The progress of the pregnancy must be followed until the outcome of the pregnancy is known (i.e., delivery, elective termination, or spontaneous abortion). If the pregnancy results in the birth of a child, additional follow-up information may be requested.

The Investigator will be asked to obtain follow-up information no later than 2 months after the gestational period to obtain maternal/fetal/neonatal outcome and any other relevant information.

Follow-up information may be requested at additional time points. All study-related contacts involving a known pregnancy should include pregnancy status assessment until pregnancy outcome is known.

Please note that pregnancy in and of itself is not an AE or an SAE. Pregnancy should not be entered into the eCRF as an AE unless the Investigator suspects an interaction between the study drug and the contraceptive method. Additionally, all information received will be assessed for any AEs and SAEs and processed per study guidelines. If the subject is discontinued because of pregnancy, pregnancy will be documented as the reason for study discontinuation. Spontaneous abortions and stillbirths will be reported as SAEs.

#### **7.2.6 IND Safety Report**

The sponsor must notify FDA and all participating investigators (i.e., all investigators to whom the sponsor is providing drug under its INDs or under any investigator's IND) in an IND safety report of potential serious risks, from clinical trials or any other source, as soon as possible, but in no case later than 15 calendar days after the sponsor determines that the information qualifies for reporting under **Sections 7.2.6.1. to 7.2.6.3.** below. In each IND safety report, the sponsor must identify all IND safety reports previously submitted to FDA concerning a similar suspected adverse reaction, and must analyze the significance of the suspected adverse reaction in light of previous, similar reports or any other relevant information.

##### **7.2.6.1 Serious and unexpected adverse reaction**

The sponsor must report any suspected adverse reaction that is both serious and unexpected. The sponsor must report an adverse event as a suspected adverse reaction only if there is evidence to suggest a causal relationship between the drug and the adverse event, such as:

- A single occurrence of an event that is uncommon and known to be strongly associated with drug exposure (e.g., angioedema, hepatic injury, Stevens-Johnson Syndrome);
- One or more occurrences of an event that is not commonly associated with drug exposure, but is otherwise uncommon in the population exposed to the drug (e.g., tendon rupture);
- An aggregate analysis of specific events observed in a clinical trial (such as known consequences of the underlying disease or condition under investigation or other events that commonly occur in the study population independent of drug therapy) that indicates those events occur more frequently in the drug treatment group than in a concurrent or historical control group.

#### **7.2.6.2 Findings from other studies**

The sponsor must report any findings from epidemiological studies, pooled analysis of multiple studies, or clinical studies (other than those reported under section 7.2.6.1), whether or not conducted under an IND, and whether or not conducted by the sponsor, that suggest a significant risk in humans exposed to the drug. Ordinarily, such a finding would result in a safety-related change in the protocol, informed consent, investigator brochure (excluding routine updates of these documents), or other aspects of the overall conduct of the clinical investigation.

#### **7.2.6.3 Findings from animal or *in vitro* testing**

The sponsor must report any findings from animal or in vitro testing, whether or not conducted by the sponsor, that suggest a significant risk in humans exposed to the drug, such as reports of mutagenicity, teratogenicity, or carcinogenicity, or reports of significant organ toxicity at or near the expected human exposure. Ordinarily, any such findings would result in a safety-related change in the protocol, informed consent, investigator brochure (excluding routine updates of these documents), or other aspects of the overall conduct of the clinical investigation.

#### **7.2.6.4 Increase rate of occurrence of serious suspected adverse reactions**

The sponsor must report any clinically important increase in the rate of a serious suspected adverse reaction over that listed in the protocol or investigator brochure.

#### **7.2.6.5 Submission of IND safety reports**

The sponsor must submit each IND safety report in a narrative format or on FDA Form 3500A or in an electronic format that FDA can process, review, and archive. FDA will periodically issue guidance on how to provide the electronic submission (e.g., method of transmission, media, file formats, preparation and organization of files). The sponsor may submit foreign suspected adverse reactions on a Council for International Organizations of Medical Sciences (CIOMS) I Form instead of a FDA Form 3500A. Reports of overall findings or pooled analyses from published and unpublished in vitro, animal, epidemiological, or clinical studies must be submitted in a narrative format. Each notification to FDA must bear prominent identification of its contents, i.e., "IND Safety Report," and must be transmitted to the review division in the Center for Drug Evaluation and Research or in the Center for Biologics Evaluation and Research that has responsibility for review of the IND. Upon request from FDA, the sponsor must submit to FDA any additional data or information that the agency deems necessary, as soon as possible, but in no case later than 15 calendar days after receiving the request.

